## 5.6 Patient-Reported Outcomes Administration

A detailed description of the PRO measures to be administered has been included in Section [6.2](#).

- 5.6.1 PRO Instruments to be administered:
- 1) The Functional Assessment of Cancer Therapy–General (FACT-G); 27 items
  - 2) The PROMIS Fatigue 7-item Short Form
  - 3) The Functional Assessment of Anorexia/Cachexia Treatment (FAACT; 12 items)
  - 4) Functional Assessment of Chronic Illness Therapy-Diarrhea (FACIT-D; 11 items)
  - 5) FACT-Breast Symptom Index (FBSI; 8 items) – taken from 8-item FBSI outlined by Yost et al that has event-based anchor points
  - 6) Medication Adherence Scale

Rev. Add7

- 5.6.2 PRO-CTCAE items to be administered:  
Select PRO-CTCAE items (16 items) will be administered to measure patient reporting of AEs.

Rev.4/15

- 5.6.3 Patient-Reported Outcomes Assessment Schedule
- 5.6.3.1 Brief symptom index to evaluate TTD: we plan to use 6 items from the FBSI -- FACT Breast Symptom Index to detect symptom deterioration. These 6 items have been selected to focus on proximal change in symptoms. However, we will collect all 8 of the items from the FBSI 8 outlined by Yost et al. These items will be administered at the following times:
- 1) Baseline (before Cycle 1 Day 1)

- 
- 2) End of Every Cycle for Cycles 1-6
  - 3) End of Cycles 8, 10, and 12
  - 4) Then administered on the same schedule as tumor assessments until disease progression (Note, for FBSI there are not assessments planned at or post progression).
- 5.6.3.2 PRO measures of treatment toxicities (PROMIS Fatigue, FAACT, FACIT-D) will be administered at the following time points:
- 1) Baseline (before Cycle 1 Day 1)
  - 2) End of Cycle 3
  - 3) End of Cycle 6
  - 4) End of Cycle 12
  - 5) At end of protocol treatment, including treatment discontinuation for any reason (i.e. toxicity, progression, completion of protocol therapy)
  - 6) 4-weeks after end of protocol treatment, including treatment discontinuation for any reason (i.e. toxicity, progression, completion of protocol therapy).
- Rev. Add7 5.6.3.3 The ECOG-ACRIN Medication Adherence Scale Modified from the Morisky Index will be administered:
- 1) End of Cycle 3
  - 2) End of Cycle 6
  - 3) End of Cycle 12
  - 4) At end of protocol treatment, including treatment discontinuation for any reason (i.e. toxicity, progression, completion of protocol therapy)
- 5.6.3.4 Patient-reported HRQL will be assessed using the FACT-G and will be administered:

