- 1) Baseline (before Cycle 1 Day 1)
  - 2) End of Cycle 3
  - 3) End of Cycle 6
  - 4) End of Cycle 12
  - 5) At end of protocol treatment, including treatment discontinuation for any reason (i.e. toxicity, progression, completion of protocol therapy)
- Rev. Add5 5.6.3.5 PRO-CTCAE: PRO-CTCAE items will be administered
- 1) Baseline and prior to every cycle, following the same schedule as trial symptom/toxicity assessments.
  - 2) End of each Cycle during treatment
-

- 3) At end of protocol treatment, including treatment discontinuation for any reason (i.e. toxicity, progression, completion of protocol therapy)

**NOTE:** The PRO-CTCAE should be completed each time a Symptom/Toxicity Assessments is completed.

The total length of this assessment is dependent on the assessment time point. One of the lengthiest assessments will occur at Baseline (FACT-G, PROMIS-fatigue, FAACT-subscale, FACIT-diarrhea subscale, FBSI, PRO-CTCAE) is 80 multiple choice items. The anticipated time to complete all items is roughly 15-20 minutes. Assessments prior to cycles 4, 7 and 13 will also include the ECOG-ACRIN Medication Adherence Scale Modified from the Morisky Index that will include 8 multiple choice or yes/no items and will take roughly 2-3 minutes. This assessment schedule corresponds to the first, second, and fourth disease assessments. We have scheduled PRO assessments with standard clinic office visits to minimize participant and site burden, thus minimizing the risk of missing PRO data. Assessments to be administered at every cycle (FBSI, PRO-CTCAE) will include 21 multiple choice items and will take 4-5 minutes to complete.

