PROMIS Fatigue, FAACT, FACIT-D: Baseline (before Cycle 1 Day 1), end of Cycle 3, end of Cycle 6, end of Cycle 12, at end of protocol treatment, including treatment discontinuation for any reason (i.e., toxicity, progression, completion of protocol therapy) and 4 weeks after end of protocol treatment, including treatment discontinuation for any reason (i.e., toxicity, progression, completion of protocol therapy).

Rev. 10/16 The ECOG-ACRIN Medication Adherence Scale Modified from the Morisky Index: end of Cycle 3, end of Cycle 6, end of Cycle 12, and at  
Rev. Add7 end of protocol treatment, including treatment discontinuation for any reason (i.e. toxicity, progression, completion of protocol therapy).  
Please note there will be one Medication Adherence Scale form completed for each agent (entinostat/placebo and exemestane).

FACT-G: Baseline (before Cycle 1 Day 1), end of Cycle 3, end of Cycle 6, end of Cycle 12, and at end of protocol treatment, including treatment discontinuation for any reason (i.e. toxicity, progression, completion of protocol therapy).

8. The FBSI will be administered at baseline, end of each cycle for the first six months after randomization, and then at the end of Cycles 8, 10, and 12. After Cycle 12, the FBSI will be administered on the same schedule as Tumor assessments until disease progression.
9. Pill counts for entinostat/placebo and diaries for exemestane should be collected at the end of each cycle until discontinuation of study treatment.
10. Repeat any test not done  $\leq$  the prior 28 days.
11. Every 3 months if patient is  $< 2$  years from study entry, every 6 months if patient is 2-5 years from study entry, and annually if patient is  $>5$  years from study entry. No specific requirements if patient is more than 10 years from study entry.
12. Tumor assessments are to be done up to (and including) the assessment which shows first progression of disease. If patient discontinues treatment due to reasons other than disease progression, concomitant medication and tumor assessments should be performed until disease progression on the following schedule: Every 3 months if patient is  $< 2$  years from study entry, every 6 months if patient is 2-5 years from study entry, and annually if patient is  $>5$  years from study entry. No specific requirements if patient is more than 10 years from study entry.

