#### 9.6.2 Analysis plan for PROs

The analysis time for PROs endpoints is at about 40 months (24 months of accrual + 12 months of treatment + 1 month follow up after treatment + 3 months of data collection and cleaning) after study activation. Subscale scores for all endpoints will be prorated by multiplying the sum of the subscale by the number of items in the subscale, then dividing by the number of items actually answered: Prorated subscale score = (sum of items cores) \* (number of items in subscale) / (number of items answered). When there are missing data, prorating by subscale in this way is acceptable as long as more than 50% of the items are answered in each subscale. For overall QOL, the FACT-G scale is considered to be an acceptable indicator of patient quality of life as long as overall item response rate is greater than 80%. For the four symptoms, the measurement scales (i.e., PROMIS-Fatigue, FAACT-Additional Concerns subscale, FACIT-Diarrhea) must be completed over 50% of the items (e.g., 4 of 7 items, 6 of 11 items and 7 of 12 items) in order to consider each subscale score valid.

Standard descriptive and graphical analyses will be used initially to examine missing data patterns, and to understand the relationship between variables. The assessment scores for the four symptoms and HRQL will be compared between the two treatment arms at baseline, month 3, month 6, month 12, at the end of protocol treatment and 4-week post-treatment (regardless of the reasons for off treatment), using two independent samples t test (or Wilcoxon rank sum test if the distribution of the score is not symmetric). Change in the four symptoms and HRQL between month 3 visit and the baseline visit will be compared between the two arms using two independent sample t tests. Similar analyses will be conducted for each FACT-G subscales as well. The mean score and proportion of moderate/severe symptoms will be compared between treatment arms for each individual FACT-G item at month 3 using Wilcoxon rank sum test and Fisher exact test, respectively, as an exploratory analysis.

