#### 9.7.2 Analysis plan for adherence

The analysis time for adherence endpoint is at about 70 months after study activation (same time as final OS analysis). All patients who receive at least one dose of protocol therapy and have sufficient adherence data will be included in the analysis.

The distribution of the adherence score for each agent will be displayed via box-and-whisker plot. The proportion of high, medium and low adherence to each agent will be calculated along with the binomial exact 95% confidence interval. The proportion of high adherence to entinostat and placebo will be compared between arms A and B using Fisher exact test. The proportion of adherence to exemestane will be compared between treatment arms using Fisher exact test as well. In addition, the adherence score for each cycle will be calculated for each agent and plot by treatment cycle to examine how adherence changes over time. The reasons for non-adherence will be summarized for each agent on each arm. The agreement on adherence level during a treatment period will be examined between the pill counts method and the Medication Adherence Scale method.

As an exploratory analysis, the association between baseline HRQL (categorized as good, fair, poor) and adherence to protocol therapy (categorized as high, medium and low adherence or dichotomized as good or poor) during the whole treatment period will be examined in each treatment arm using Fisher exact test. Multivariable logistic regression analysis will be conducted to identify the baseline factors which can predict high adherence. The covariates will include HRQL and other patient demographics and disease characteristics, such as age at diagnosis, ECOG PS, disease stage, prior therapy, et al.

The association between adherence to protocol therapy during the whole treatment period (categorized as high, medium or low) and HRQL (continuous score) at one-month after treatment discontinuation will be examined using ANOVA test and linear regression analysis, adjusting for HRQL at baseline and other demographic and disease characteristics.

Another exploratory analysis is to examine the association between the occurrence of toxicity in the first two cycles and adherence to entinostat after cycle 2 in patients on arm A.

In all analyses, P-values will be two-sided. A level of 5% will be considered statistically significant. No adjustment will be made for multiple comparisons.

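### The plan contradicts itself on whether FACT-G is given 4 weeks after end of treatment, a form that two of its quality-of-life analyses need

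*Combined protocol and SAP*

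**What the plan says.** Two places schedule FACT-G by instrument. Section 5.6.3.4 begins "Patient-reported HRQL will be assessed using the FACT-G and will be administered", and its last entry is "5) At end of protocol treatment, including treatment discontinuation for any reason". Section 7, footnote 7, repeats the list: "FACT-G: Baseline (before Cycle 1 Day 1), end of Cycle 3, end of Cycle 6, end of Cycle 12, and at end of protocol treatment". Neither goes further for FACT-G. For PROMIS Fatigue, FAACT and FACIT-D, both places do: Section 5.6.3.2 has the entry "6) 4-weeks after end of protocol treatment, including treatment discontinuation for any reason", and footnote 7 has "and 4 weeks after end of protocol treatment, including treatment discontinuation for any reason".

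The statistical section reads differently. Section 9.6 gives one general PRO schedule running to 4 weeks after discontinuation and exempts only the FBSI and the Medication Adherence Scale. Section 9.6.2 says "The assessment scores for the four symptoms and HRQL will be compared between the two treatment arms at baseline, month 3" and, after months 6 and 12, "at the end of protocol treatment and 4-week post-treatment (regardless of the reasons for off treatment". Section 9.7.2 relates adherence to a later outcome: "HRQL (continuous score) at one-month after treatment discontinuation will be examined using ANOVA test and linear regression analysis". The rationale that closes Section 5.6.3 twice names HRQL as a purpose of the assessments at and after end of treatment.

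**The concern.** An analysis at a given time point needs a form collected at that time point. HRQL in this trial is FACT-G: Section 6.2.1 names it as the measure, and Section 9.6.1 builds the Trial Outcome Index from its physical and functional items. If sites follow the instrument lists, two planned analyses have no outcome data.

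The gap falls where the plan says it matters. Section 5.6.3 argues that scores taken only from patients still on treatment will look too favourable, and it relies on post-treatment assessment to correct this. A 4-week HRQL comparison that quietly drops out would also be an unexplained departure from the plan at reporting.

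**Working it through.** **1. Time points side by side.**

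| Time point | FACT-G lists (5.6.3.4; 7, fn 7) | Fatigue, FAACT, FACIT-D lists (5.6.3.2; 7, fn 7) | General schedule (9.6) | HRQL analysis (9.6.2) |
|---|---|---|---|---|
| Baseline | yes | yes | yes | yes |
| Month 3 | yes | yes | yes | yes |
| Month 6 | yes | yes | yes | yes |
| Month 12 | yes | yes | yes | yes |
| End of treatment | yes | yes | yes | yes |
| 4 weeks after | **no** | yes | yes | yes |

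The FACT-G lists have 5 time points and the HRQL analysis has 6. Section 9.7.2 needs the missing one.

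**2. Does Section 9.6 include FACT-G?** Section 5.6.1 lists six PRO instruments. Removing the two that 9.6 exempts leaves FACT-G, PROMIS Fatigue, FAACT and FACIT-D. Read literally, 9.6 therefore schedules FACT-G at 4 weeks. The conflict is between two schedules as well as between a schedule and an analysis.

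**3. Can another instrument supply the score?** No. The three forms given at 4 weeks cover fatigue, appetite and nausea, and diarrhea (Section 6.2.2). The FBSI is a symptom index with no assessment planned at or after progression (Section 5.6.3.1).

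**4. Patients affected.** Section 9.6 limits PROs to treated patients among the first 360. Section 9.3.3 assumes 9 of 180 per arm never start: 2 × (180 − 9) = 342. This is an upper figure for the expected number of 4-week forms. Deaths, unreturned forms and patients still on treatment at the PRO analysis (about month 40) reduce it.

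No patient number is given here for the 9.7.2 analysis. The 80% with adherence data in Section 9.7.1 refers to all 300 arm A patients, whereas PROs stop at the first 360, and 9.7.2 does not say whether the arms are pooled.

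**5. Primary PRO comparison.** The inputs in Section 9.6.1 are a difference of 5, SD 12, 162 per arm and two-sided alpha 0.025. The standardised difference is 5 / (12 × √(2/162)) = 5 / 1.333 = 3.75. Power is 93.4% by the normal approximation and 93.2% by the noncentral t, against about 93% stated. The figure reproduces, and it uses only month-3 forms.

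**6. Burden of adding the form.** The 4-week contact now carries 7 + 12 + 11 = 30 items; with FACT-G it is 30 + 27 = 57. At the protocol's rate of 80 items in 15 to 20 minutes, the addition takes 27 × 15/80 = 5.1 to 27 × 20/80 = 6.8 minutes.

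**The case against.** The best defence of the lists is that they are deliberate. FACT-G is left out at 4 weeks in both places while three other instruments are included, and Section 5.6.3 gives a symptom-specific reason for the 4-week form: whether entinostat-related symptoms have resolved. The calendar cross under Post treatment does not help the other side, because footnote 7 defines that row by instrument. Section 9.6 could also be called a loose summary, since Section 6.2.2.4 counts PRO-CTCAE among the PRO endpoints and 9.6 does not mention its different schedule.

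Some of this stands: the omission is consistent across both lists and may have been intended. But PRO-CTCAE is listed apart from the six PRO instruments (Section 5.6.2) and has its own calendar row, so the exemptions in 9.6 are complete on that classification. A reader might infer from the lists that FACT-G is scheduled nowhere at 4 weeks, or that the text is evenly divided. Neither reading is supported. Section 9.6, the two HRQL statements in the 5.6.3 rationale, 9.6.2 and 9.7.2 all point to collection, against two near-identical lists.

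It is also fair to say that little depends on this. No power is claimed for HRQL at 4 weeks, the 9.7.2 analysis sits among those labelled exploratory, and FACT-G at end of treatment remains planned.

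**Conclusion.** The contradiction is real and rests on the text alone; confidence in it is high. Its severity is minor. At risk are one of six HRQL time points in Section 9.6.2, involving at most about 342 expected patients under the plan's 5% non-start assumption, and the HRQL-outcome analysis in Section 9.7.2. The month-3 comparison, which Section 9.6 makes primary for PROs, keeps its data and its power.

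A reader might infer that the 4-week HRQL data have been lost. The documents do not show that. Section 13 refers the forms schedule to the E2112 Forms Completion Guidelines, which are not among the documents and may include the form. Nor do the documents say whether PRO collection in the first 360 patients is finished.

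**What to change.** First establish whether PRO collection in the first 360 patients is still open, and count the 4-week FACT-G forms already held.

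- **If collection is open:** the weight of the text favours collecting. Add to the FACT-G lists in Section 5.6.3.4 and footnote 7 the same 4-week entry that the other three instruments carry, and check that the Forms Completion Guidelines agree. The 4-week contact exists, and Section 5.6.4 already provides the mail and telephone procedure. The cost is 27 more items, about 5 to 7 minutes, for patients who have just stopped treatment. No new contact is needed, but this is a small change in data collection and not only in wording.
- **If collection is complete, or the form is not wanted:** remove 4-week HRQL from Sections 9.6, 9.6.2 and 9.7.2, and align the Section 5.6.3 rationale. Report how many 4-week FACT-G forms exist, or that these analyses were not done. The cost is the HRQL comparison after end of treatment and the analysis of adherence against later HRQL.

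Neither route changes a sample size or a power figure.

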**Agent Accountability and Availability**

Entinostat and matching Placebo (IND# [REDACTED]) will be provided free of charge by Syndax Pharmaceuticals and distributed by the Pharmaceutical Management Branch (PMB), Cancer Therapy Evaluation Program (CTEP), Division of Cancer Treatment and Diagnosis (DCTD), National Cancer Institute (NCI).

Rev. 10/16

Entinostat is supplied by the Syndax Pharmaceuticals, Inc. and distributed by DCTD, NCI as 1 mg (pink to light red, in bottles of 15 tablets), or 5 mg (yellow, in bottles of 5 tablet) film-coated tablets (round-biconvex). Each tablet also contains mannitol, sodium starch glycolate, hydroxypropyl cellulose, potassium bicarbonate, and magnesium stearate. The film coating consists of hypromellose, talc, titanium dioxide, and ferric oxide pigments (red and yellow) as colorants.

Matching placebo for entinostat has the same appearance as the corresponding active tablets and contains the same inactive ingredients and film coating.

**NOTE:** Under no circumstances can commercially supplied Entinostat be used or substituted for the NCI-supplied Entinostat/Placebo.

Commercial exemestane will be provided free of charge by Syndax Pharmaceuticals. In the United States it will be distributed by the Pharmaceutical Management Branch (PMB), Cancer Therapy Evaluation Program (CTEP), Division of Cancer Treatment and Diagnosis (DCTD), National Cancer Institute (NCI). Outside of the United States, distribution will be arranged by Syndax Pharmaceuticals.

Each tablet is round, biconvex, and off-white to slightly gray. Exemestane is packaged in HDPE bottles with a child-resistant screw cap, 30 tablets per bottle. Exemestane tablets contains the following inactive ingredients: mannitol, crospovidone, polysorbate 80, hypromellose, colloidal silicon dioxide, microcrystalline cellulose, sodium starch glycolate, magnesium stearate, simethicone, polyethylene glycol 6000, sucrose, magnesium carbonate, titanium dioxide, methylparaben, and polyvinyl alcohol. [Pfizer, Package Insert]

**Drug Orders, Transfers, Returns, Accountability and Emergency Unblinding**

**No blinded starter supplies will be available for this study.**

Once a patient has been randomized, blinded, patient specific supplies will be sent automatically to the registering investigator and should arrive within 10 days. Study drug requests are transmitted by the ECOG-ACRIN Operations Office – Boston the day the patient is randomized and will be processed by PMB the next business day and shipped the following business day. Shipments within the United States are sent by FedEx ground (generally three to five day delivery) and shipments to Canada are sent by FedEx (generally one to two day delivery) Thus, if a patient is registered on Monday, ECOG-ACRIN would enter a clinical drug request for that patient on Monday and PMB would process that request on Tuesday and ship the drug on Wednesday. United States

sites could expect to receive their order approximately Wednesday. Shipments to United States sites can be expedited (i.e., receipt on Thursday in example above) by the provision of an express courier account name and number to the ECOG-ACRIN Operations Office – Boston at the time the patient is randomized.

The initial request will be for 3 bottles of Entinostat or matching placebo. Ten (10) weeks after the initial electronic request [i.e., two (2) weeks before needed], sites may reorder an additional 3 bottles of Entinostat or matching placebo by using the PMB Online Agent Order Processing (OAOP) application (<https://eapps-ctep.nci.nih.gov/OAOP/pages/login.jsp>). Access to OAOP requires the establishment of a CTEP Identity and Access Management (IAM) account (<https://eapps-ctep.nci.nih.gov/iam/>) and the maintenance of an “active” account status and a “current” password. The assigned patient ID number (e.g., "999999") and the patient initials (e.g., "L,FM") must be entered in the "Patient or Special Code" field. A separate order is required for each patient ID number (e.g., "999999") being ordered. All drug orders will be shipped directly to the physician responsible for treating the patient.

Each blinded, patient -specific bottle will be labeled with:

- The protocol number (i.e., “E2112”)
- The bottle number (i.e., “Bottle 1 of 3, 2 of 3, 3 of 3”)
- The number of tablets (i.e., “5 tablets” or “15 tablets”)
- The patient ID number (e.g., "44444", where “44444” represents a unique patient identifier assigned at randomization)
- The patient initials (i.e., first initial, last initial [e.g., "FL"])
- The agent identification (i.e., “Entinostat 5 mg or placebo”)
- A blank line for the pharmacist to enter the patient’s name
- Administration instructions
- Storage instructions (i.e., Store at 25°C (77°F), excursions permitted from 15°C to 30° C (59-86 °F) )
- Emergency contact instructions
- A Julian date

The Julian date indicates the day the bottles were labeled and shipped and is composed of the last two digits of the calendar year (e.g., 2013 = 13, 2014 = 14) and a day count (e.g., January 1 = 001, December 31 = 365). For example, a bottle labeled and shipped on January 1, 2013 would have a Julian date of ‘13001’ and a bottle labeled and shipped on December 31, 2013 would have a Julian date of ‘13365’. The Julian date will be used by PMB for recalls. When a lot expires, PMB will determine the last date the expired lot was shipped and will recall all bottles shipped on or before that date thus eliminating any chance of breaking the blind.

